Split-belt treadmill walking, whereby the walking speed of each leg can be manipulated independently, is a useful tool to study both motor switching and modulating gait asymmetry. In a recent study at our lab, motor switching ability during different asymmetric split-belt conditions was studied in patients with and without FOG. It was shown that non-freezers were **able to adapt spatial gait symmetry** to different switching split-belt conditions similarly as healthy controls. However, **adaptive capacity was reduced in freezers** (figure 1A) [18]. The powerfulness of the split-belt paradigm was also confirmed by the fact that immediately after the switch, FOG was evoked in two cases. In another study from the group at Christian-Albrechts University Kiel (CAUK), Germany, the **short-term effects of 10 minutes split-belt walking** were studied through reducing the belt velocity of either the body side with the longer or shorter step length in PD. **Gait asymmetry, bilateral coordination and the consecutive reduction in step lengths were improved** in the tied-belt condition after subjects walked with reduced velocity at the side with the longer step length ("better side reduction") (figure 1B) [19]. These exciting pilot results provide **proof-of-principle evidence** for the current project. To consolidate these findings, our research group in collaboration with the group at Kiel will undertake two studies, probing short term motor adaptation (present study) and prolonged motor learning (future study) to alleviate freezing-related gait deficits.

[figure not shown]

Figure 1. A) Impaired adaptive capacity of patients with PD with FOG during split-belt gait (data from KUL: mod. according to Mohammadi et al. 2015); B) Step length during baseline, early and late split-belt adaptation (25% reduced belt's speed of the leg with the longer step length (best-side reduction)) and after effect (data from CAUK: mod. according to Fasano et al. 2016).

IV. Study objectives

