We hypothesize that being exposed to larger contrasts between split-belt speeds (ratio) will result in improved gait symmetry and better savings in motor memory, thus leading to better retention effects and this more so in controls than in PD. We also hypothesize that variable split-belt conditions (changing ratios) will lead to better adaptive capacity to transitions than steady split-belt walking with a consistent ratio.

V. Methodology of the research

Number of participants: This pilot study investigating the short-term effects of split-belt walking on gait asymmetry and motor learning is conducted in collaboration with CAUK and will include a total number of 128 participants i.e 64 at each centre comprising 32 patients with PD and 32 healthy controls.

Recruitment: Older adults will be recruited from an existing database of healthy volunteers. Recruitment of PD patients will be conducted via a database of patients that has been built up over the years in our laboratory in collaboration with the neurologist at the Movement Disorders clinic at UZ Leuven ([name]. [name]). Flyers containing study information will be handed to people expressing interest to participate.

Inclusion and Exclusion Criteria: PD patients with FOG who can walk at least 5 minutes at a stretch will be included in this study. Exclusion criteria are: participation in treadmill training in the 3 months prior to the study, other neurological impairments, orthopedic injuries that could influence gait or balance, cardiovascular exercise risk factors, dementia or self-reported DBS-related postural or gait disturbances.

Design: Patients will be tested in the ON phase of medication on consecutive days in a session of about 2 hours. Figure 2 shows that the included subjects will be randomized into 4 treatment groups to compare the impact of different (3:4 and 1:2) and changing ratios of split-belt walking relative to traditional treadmill training (Tied-Belt). Effects will be analysed pre-post (I-II) and after 24 hours (III) retention. The second training session (III-IV) will explore the possible benefits of repeated training and serves as a pilot for a larger training study.

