Standardization: Testing and training methods and protocol as well as patient instructions will be standardised across the two centres by documentation of procedures as well as through regular communication. Researchers from both groups will attend initial measurements and in addition, during the first 3 months of the project, a monthly skype call between researchers will be held to check the fidelity of procedures and ensure adherence.

[figure not shown]

Figure 2. Study design. 128 participants will be recruited across the two centres and data will be pooled for analysis. SBT, Split-belt Treadmill; PD, Parkinson's disease; HC, healthy control.

Intervention

Participants will first walk normally (5 x 5m) at a comfortable pace to assess **overground walking speed** and to assess which leg has the longer/shorter step length. **Best/worst side** will be further confirmed with a toe-tapping test and by asking the PD patients about their more/less affected PD side. Next, participants will walk on the treadmill for a maximum of 3 minutes to get familiar with treadmill walking, reaching their overground gait speed. Intervention will consist of one training session of 6 x 5 min. treadmill gait with 1 min. rest in between [12]. Participants are not allowed to walk overground during the rest but a chair will be provided if necessary. Subjects are wearing a harness to prevent falling. Belt speed will be adjusted according to the individual's comfortable overground gait velocity. Previous studies have shown **improved gait symmetry after split-belt conditions with slower belt speed of the side with the longer step length ('best side reduction')** in PD and stroke [19, 23]. As it has been shown that belt speed ratio but not absolute speed impacts on gait asymmetry (unpublished data), we chose to decrease the belt speed of the side with the longer step length rather than increasing the belt speed of the side with the shorter step length. Also, to avoid hastening, the 'best side reduction' principle will be adopted using a 3:4 or 1:2 ratios (table 1).

Table 1: Belt speed of the 4 treatment groups

Group	Belt speed ratio	Belt speed of the leg with the longer step length (% of overground gait speed)	Belt speed of the leg with the shorter step length (% of overground gait speed)
A-Steady Split-belt Treadmill	3:4	75%	100%
B-Steady Split-belt Treadmill	1:2	50%	100%
C-Transfer Split-belt Treadmill	changing	50-75%	100%
D-Treadmill (tied-belt)	1:1	100%	100%

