Outcome Measures

Laboratory FOG assessment: A FOG ratio score will be calculated [24]. FOG will be analysed with accelerometer sensors (APDM) during FOG provoking tasks (360° turning in place (right/left side alternating) for 1 minute with and without a cognitive dual task.

Overground gait analysis: the following gait variables will be analysed during 5 trials of 5m gait with comfortable pace (assessed via accelerometer sensors (APDM) and Vicon/Qualisys motion capture analysis): step length, gait asymmetry, gait variability, bilateral coordination [25] and gait velocity.

Treadmill gait analysis: adaptive capacity during transitions will be assessed by analysing the above mentioned variables during changing split-belt conditions. Retroreflective markers will be placed bilaterally on the limbs to allow gait analysis at 100Hz with infrared cameras.

Descriptors: MDS-Unified Parkinson's Disease Rating Scale (MDS-UPDRS) [26], New Freezing of Gait Questionnaire [27], Mini Mental State Exam (MMSE) [28], Montreal Cognitive Assessment (MoCA) [29], Frontal Assessment Battery, Falls Efficacy Scale International (FES-I), Mini-BESTest [30], Borg Rating of Perceived Exertion, Visual Analogue Scale for fatigue and number of falls during the last 6 months.

VI. Planned Statistical analysis & Data Management

Data storage: Part of the data obtained on paper (e.g. questionnaires, informed consent forms) will be stored in an excel file. The data obtained by computerized measures will all be stored in the original digital files, and the main variables will be stored in excel datafiles. All data will regularly be backed up to a secure KU Leuven server.

Statistics: Data from both centres will be pooled for the statistical analysis. The immediate effects and short term (24 hour) retention of split-belt treadmill training on overground gait symmetry and the freezing ratio during the turning task are the **main outcomes of interest**. Repeated measures ANOVA with group and training condition as between subjects factors will be employed in order to test this. Effect sizes will be determined and a post-hoc power calculation will be performed to ascertain sample sizes for a planned larger training study.

VII. Safety

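### If the planned repeated measures ANOVA spans I, II and III as one model, a participant who misses day 2 is dropped from the immediate (I-II) comparison as well

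*Protocol*

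**What the plan says.** The Statistics paragraph of section VI identifies the main outcomes as "The immediate effects and short term (24 hour) retention of split-belt treadmill training on overground gait symmetry and the freezing ratio during the turning task". The next sentence gives the method: "Repeated measures ANOVA with group and training condition as between subjects factors will be employed in order to test this". It states the between-subject factors but not the levels of the time factor.

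The Design paragraph of section V describes the visits. Testing takes place on consecutive days: "Effects will be analysed pre-post (I-II) and after 24 hours (III) retention". Of the second day's training it says: "The second training session (III-IV) will explore the possible benefits of repeated training and serves as a pilot for a larger training study". So I and II fall on day 1, III needs a return the next day, and IV is exploratory.

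The sample is stated as follows: the study "will include a total number of 128 participants i.e 64 at each centre comprising 32 patients with PD and 32 healthy controls". Participants are randomised to four training conditions. No allocation ratio and no expected loss are given.

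**The concern.** A classical repeated measures ANOVA needs a value at every level of the within-subject factor. Anyone with a gap is removed from the whole analysis, including contrasts for which that person has complete data. Here the two main contrasts sit on different days. If one model covers I, II and III, someone with I and II observed who does not come back leaves the I-II comparison even though nothing is missing from it. If IV were also a level, a person with I, II and III but no IV would be lost from both main contrasts because of an exploratory measurement.

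The protocol fixes this method itself, and the method decides who is analysed, so the point is more than a detail left for an SAP. Two things are at stake. The first is precision, in cells that are already small. The second, under further conditions, is a distorted comparison between training conditions. The second research question in section IV uses that comparison to choose a condition for long-term training, and section VI uses the effect sizes to size the larger study.

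**Working it through.** **Inputs from the protocol.** Two centres, each with 32 PD patients and 32 controls; four arms (section V and Table 1); I and II on day 1, III the next day, IV exploratory.

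**Assumed inputs.** Equal allocation; loss of III between 5% and 25%; two-sided alpha 0.05; standardised difference d = 0.8 for illustration. The protocol gives none of these.

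**1. The plan's own figure.** 2 x (32 + 32) = 128, as stated. PD patients per arm: 2 x 32 / 4 = 16. The same holds for controls. No power calculation lies behind 128, so there is none to reproduce.

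**2. Who is analysed when day 2 is missed.**

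| Analysis | Kept for I-II? | Kept for I-III? |
|---|---|---|
| One classical ANOVA over I, II, III | No | No |
| Separate ANOVAs, I-II and I-III | Yes | No |
| Mixed model on all available data | Yes | Contributes through I and II |

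If IV is added as a level to the first row, a person who misses only IV is also lost from both contrasts.

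**3. Precision.** The variance of an arm contrast is proportional to 1/n, so losing a share p multiplies it by 1/(1 - p).
- p = 0.10: 16 x 0.10 = 1.6 patients per arm lost; 1/0.90 = 1.11, a rise of 11%.
- p = 0.20: 16 x 0.20 = 3.2 patients per arm lost; 1/0.80 = 1.25, a rise of 25%.

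Power for one PD arm against another, by the normal approximation Φ(d / √(2/n) - 1.96), at d = 0.8:
- n = 16: 0.62
- n = 14.4 (10% loss): 0.57
- n = 12.8 (20% loss): 0.53

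**4. Bias.** Simulation with no true arm difference, SD 1 at each visit and equal correlation r between visits. III is missing with a probability that rises as the I-II change gets worse (logistic slope 1 per SD of that change). One arm loses 25%, the other 5%.

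| r | False I-II difference, complete cases | False I-III difference, complete cases | Both, all observed data |
|---|---|---|---|
| 0.5 | 0.17 SD | 0.08 SD | about 0 |
| 0.7 | 0.13 SD | about 0.06 SD | about 0 |
| 0.9 | 0.07 SD | 0.04 SD | about 0 |

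The I-III bias is half the I-II bias because the regression of the I-III change on the I-II change has slope (1 - r) / (2(1 - r)) = 0.5.

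For scale at r = 0.5, the SD of the change is √(2(1 - 0.5)) = 1. With 12 and 15.2 patients left, the standard error of the arm difference is √(1/12 + 1/15.2) = 0.39. The I-II bias is thus about 0.43 of a standard error, and the I-III bias about 0.22.

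**5. When the bias vanishes.** With 10% loss in both arms it is about 0, even though poorer responders are the ones lost. It is also about 0 when loss is unrelated to response, whatever the rates. At 10% versus 5% with the same dependence on response, it is about 0.02-0.04 SD on I-II.

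**The case against.** The strongest reply is that the protocol never says one model spans all visits. The Design paragraph names the I-II effect and 24-hour retention as separate effects. Two separate ANOVAs would fit both sections, and missing day 2 would then cost the immediate result nothing. This stands, and it makes the point conditional. It does not remove it: section VI names the two outcomes together with one method, and separate ANOVAs would still leave the retention analysis to complete cases.

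A reader might infer two stronger claims. The protocol supports neither.

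- *Anyone who stops training is lost.* Stopping a session is not the same as missing an assessment. Nothing says that someone who ends training early skips II or III, and a person measured at both stays in the ANOVA. If II itself is not measured, no model recovers that observation.
- *Stopping is likely to differ by arm.* The arms have different belt speeds (Table 1), but no rates of stopping are given. The remark in section III that "immediately after the switch, FOG was evoked in two cases" concerns an earlier study and reports freezing, not withdrawal. Nor is the entry criterion, "PD patients with FOG who can walk at least 5 minutes at a stretch will be included in this study", clearly at odds with the load, "Intervention will consist of one training session of 6 x 5 min. treadmill gait with 1 min. rest in between": the required stretch equals the length of one bout, and section VII provides seated rests. Arm-related loss is possible, but no more than that.

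It is also fair to say that III follows within 24 hours, so loss may be small; that 25% versus 5% is a severe scenario; and that even there the bias is under half a standard error in a self-described pilot. The magnitudes below should be read in that light.

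**Conclusion.** The point holds in conditional form. If one classical ANOVA covers I, II and III, every participant without III is removed from an immediate comparison for which the data exist. Making IV a level would extend the loss to both main outcomes.

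The firm consequence is reduced precision: an 11-25% larger variance for the I-II contrast at 10-20% loss, from a base of 16 PD patients per arm under equal allocation. Bias is a further possibility that needs two conditions together, loss that differs by arm and loss that depends on response. It is about 0.07-0.17 SD on I-II and 0.04-0.08 SD on I-III in the assumed 25% versus 5% case, and about 0 with equal loss. All loss rates, correlations and slopes are assumptions. The finding is modest in size but worth acting on, because the better analysis costs almost nothing.

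**What to change.** In the Statistics paragraph of section VI, replace the repeated measures ANOVA with a likelihood-based linear mixed model for repeated measures:

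- time (I, II, III) as a factor, with group, training condition and their interactions with time;
- every randomised participant included in the allocated arm with all available assessments;
- IV left out of the model for the main outcomes and analysed separately as exploratory.

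The lesser alternative is a clause stating that I-II and I-III are analysed separately. That saves the day-1 data but leaves retention on complete cases.

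The cost is two or three sentences, slightly more analysis work and standard software. Partly trained participants stay in the comparison, which may dilute the effect a little; completers can be shown as a sensitivity analysis. The mixed model still assumes that missingness depends only on what was observed, so it reduces the risk of bias without abolishing it.

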Screeningstesten ter evaluatie van motorische en cognitieve functie bij ziekte van Parkinson

Vragenlijsten naar 'Freezing of Gait', vermoedheid en cognitie

Klinische meetsschalen ter evaluatie van evenwicht en van de ernst van de 'Freezing of Gait'

5 m stappen buiten de loopband met en zonder een dubbeltaak

Training protocol:

Loopbandtraining van 6 x 5 min. Met telkens 1 min. zittende pauze

Duur experiment:

Patiënten met Parkinson en Freezing of gait: 2 sessies van 2 uur op 2 aparte testdagen

Gezonde controles: 2 sessies van 2 uur op 2 aparte testdagen

Plaats van de experimentele sessies:

Faculteit Bewegings-en Revalidatiewetenschappen, KULeuven

III. Background and rationale

Parkinson's disease (PD) is the **second most common** neurodegenerative disease [1, 2]. It has a substantial impact on patients' quality of life as well as on the socio-economic cost for society [3]. Gait problems are very prevalent in PD and markedly reduce patients' functional independence [4]. Freezing of gait (FOG) is without doubt the most disabling gait impairment and it constitutes **an independent risk factor for falls** [5]. This complex symptom is defined as an episode of substantial reduction or complete cessation of movement despite having the intention to move [6]. Current medical and surgical treatments only partly relieve FOG [7], strongly suggesting that non-dopaminergic mechanisms mediate its occurrence [8]. Therapeutic alternatives are, therefore, **urgently needed**. A growing body of literature

suggests that exercise and **motor learning can significantly improve gait** and mobility in PD [9, 10] with long term effects ranging from 4 to 48 weeks [11].

FOG occurs when spatiotemporal motor control breaks down and is associated with gait cycle variability, **reduced stride amplitude** and hastening of gait timing. Furthermore, FOG is also related to between-limb coordination deficits and **gait asymmetry** [12-14]. The strong link between FOG and gait asymmetry [14, 15] is underscored by the fact that turning – which is a highly asymmetric task, is the most important trigger of FOG [16, 17].

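### One ANOVA error term averaged over freezers and healthy controls can miscalibrate within-PD comparisons and the effect size used to plan the larger patient study, in a direction that depends on SDs not given

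*Protocol*

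**What the plan says.** Section V (Number of participants) plans "128 participants i.e 64 at each centre comprising 32 patients with PD and 32 healthy controls", so 64 patients and 64 controls over the two centres. The patients are all freezers: "PD patients with FOG who can walk at least 5 minutes at a stretch will be included in this study". Under Design, "the included subjects will be randomized into 4 treatment groups".

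Section VI (Statistics) sets the analysis. "Data from both centres will be pooled for the statistical analysis". The immediate and 24-hour effects on "overground gait symmetry and the freezing ratio during the turning task are the main outcomes of interest". The test is then named: "Repeated measures ANOVA with group and training condition as between subjects factors will be employed in order to test this". Since training condition is listed separately, group most naturally means PD versus control. This is an inference, because section V also uses the word for the four treatment arms.

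The next sentence gives the use of the results: "Effect sizes will be determined and a post-hoc power calculation will be performed to ascertain sample sizes for a planned larger training study". The background (section III) describes the future study as one of prolonged learning aimed at freezing-related gait deficits. The second research question (section IV) concerns the best conditions for long-term training in patients with freezing. The protocol gives no SD for either population. It does not say which effect is carried forward or which SD standardises it.

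**The concern.** An ordinary ANOVA over both populations assumes the same residual variance in all eight group-by-condition cells. Its error term estimates the average of the PD and control variances. A question about patients alone, such as which belt condition works best for them, needs the patients' own variance. If the two variances differ, the standard error of a within-PD comparison is wrong, and so is any PD effect size standardised by the pooled residual SD.

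Unequal spread is plausible here. Every patient is a freezer and every control is healthy, and one main outcome is a freezing ratio from a task meant to provoke freezing. Two things are at stake: the error rate when conditions are compared within patients, and the size of the follow-on patient study.

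**Working it through.** **Inputs from the protocol.** 2 centres × (32 PD + 32 controls) = 128; 64 PD and 64 controls; 4 conditions. There is no power calculation to reproduce.

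**Assumptions.** Equal allocation, so 64 / 4 = 16 per cell; no dropout; two-sided 5% level; 80% power for the later study. The outcome is treated as one change score per person (pre to post, or pre to 24 hours). Let r = control SD / PD SD. No SDs are given, so r is varied on both sides of 1.

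**Error degrees of freedom.** Joint model: 128 − 8 = 120. PD only: 64 − 4 = 60.

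**Pooled SD.** With equal group sizes the error variance, in units of the PD variance, is (1 + r²)/2. Therefore:
- the standard error of a within-PD contrast is multiplied by √((1 + r²)/2);
- a PD effect standardised by the pooled SD is multiplied by 1/√((1 + r²)/2);
- the sample size planned from it is multiplied by (1 + r²)/2.

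Example, r = 0.5: (1 + 0.25)/2 = 0.625; √0.625 = 0.79; 1/0.79 = 1.26.

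**True error of a nominal 5% comparison of two conditions within PD** (16 v 16, error mean square on 120 df, half from each population), by simulation:

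| r | SE factor | Effect-size factor | True error | Planned N / needed N |
|---|---|---|---|---|
| 1.25 | 1.13 | 0.88 | about 3% | 128% |
| 1 | 1.00 | 1.00 | 5% | 100% |
| 0.75 | 0.88 | 1.13 | about 8% | 78% |
| 0.5 | 0.79 | 1.26 | 12% | 63% |
| 0.3 | 0.74 | 1.35 | about 15% | 55% |

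A normal approximation agrees. The critical value on 120 df is 1.98. At r = 0.5 the effective threshold is 1.98 × 0.79 = 1.57, and a standard normal exceeds that in absolute value about 12% of the time. The limit as r goes to 0 is an effect-size factor of √2 = 1.41 and half the needed sample size.

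**Later study, true PD standardised effect 0.5 (assumed).** With the PD SD, 63 per arm give 80% power. Using the pooled SD:
- r = 0.75: 50 per arm, true power about 71%;
- r = 0.5: 40 per arm, about 61%;
- r = 1.25: 81 per arm, about 89%.

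**If the condition main effect is carried forward instead.** Let the control effect be q times the PD effect. The reported effect size relative to the true PD value is ((1 + q)/2) / √((1 + r²)/2). At r = 0.5:
- q = 0: 0.5/0.79 = 0.63;
- q = 0.5: 0.75/0.79 = 0.95;
- q = 1: 1/0.79 = 1.26;
- q = 1.5: 1.25/0.79 = 1.58.

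**PD-versus-control difference in a condition contrast.** Its true variance is (2/16)(PD variance + control variance). The model estimates (4/16) × the average of the two, which is the same quantity. Simulated error stays between 4.95% and 5.3% for r from 0 to 1.25.

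**The case against.** A reader might infer that controls certainly vary less, so that the effect sizes passed on will be too large. The protocol does not support that.
- No SD appears anywhere. The background does say "FOG occurs when spatiotemporal motor control breaks down and is associated with gait cycle variability", but that is cycle-to-cycle variability within a person. It is not the between-person SD of a training-induced change, and supports unequal spread only indirectly.
- Smaller control spread is plausible for the freezing ratio but is not stated. For gait symmetry it is less assured, since section IV expects controls to respond more strongly. If controls vary more, the bias reverses.
- Even with smaller control spread, too large is not general. If controls sit at the floor on the freezing ratio, the condition main effect is diluted and can be too small for patients (0.63 of the PD value at r = 0.5).

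A second objection is that the protocol does not commit the error. It names no within-PD contrast, effect-size measure or standardiser, and a statistical analysis plan not shown may use a PD-only SD. This stands as a limit: silence on those details is no fault. The protocol does, however, fix one joint ANOVA as its test and move directly from it to effect sizes for a larger study. The usual error term of that model is the averaged one.

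Third, this is a pilot. With 16 per arm, the 95% half-width of a PD-only standardised difference is about 2.00 × √(2/16) = 0.71. A factor of 1.13 to 1.35 moves an effect of 0.5 by only 0.07 to 0.18. That limits the practical weight, but a bias remains on top of the noise and is cheap to avoid.

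**Conclusion.** The point holds conditionally. The one model named averages two populations' variances, while the later study it is meant to inform concerns one of them. Within-PD comparisons on that error term have a true error of about 8%, 12% and 15% at SD ratios of 0.75, 0.5 and 0.3, and about 3% at 1.25. A PD effect standardised by the pooled SD is off by factors of 1.13, 1.26, 1.35 and 0.88 respectively. The sizes rest on assumed SD ratios, equal cells of 16 and group meaning PD versus control. The direction is not established by the document. A main-effect size has the further defect of including the control response. The PD-versus-control comparison of condition effects is not at issue while cells are equal. This is a worthwhile, inexpensive improvement rather than a demonstrated error in the results to come.

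**What to change.** In section VI (Statistics), state that the joint model allows separate residual variances for PD and controls, or that within-PD contrasts use a PD-only error term. Add that the sample size of the larger study will rest on the PD-specific condition effect with the PD-only SD (or the raw effect reported with that SD), and not on partial eta-squared or a condition main effect from the pooled model. This is valid at any SD ratio and needs no new data.

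The cost is one model option and one or two sentences. Error degrees of freedom for PD contrasts fall from about 120 to 60, which moves the critical value only from 1.98 to 2.00. PD effect sizes may turn out less favourable, and the larger study correspondingly bigger, if patients are the more variable group.
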